3.1.2.4. Visit 4 (Week 4 ± 3 days) (EOT for Cohorts 4-9)

Visit 4 will be conducted as an outpatient visit. The following activities will be conducted:

- Review concomitant medications for any changes
- Pregnancy test for FOCP (urine)
- Safety labs (see [Appendix 1](#) and [Appendix 3](#))
- Pharmacodynamics (ACTH, 17-OHP, A4, testosterone, and 11KT) drawn prior to GC dosing at approximately 8 AM (± 1 hour). Fasting is not required.
- Cortisol
- Tildacerfont concentration (single sample) drawn prior to GC dosing at approximately 8 AM (± 1 hour). Fasting is not required.
- GC dosing adjustments to be determined after A4 value is measured. Pre-GC A4 is drawn at visit, and once results are received Investigator or designee will call participant and advise regarding any GC dose change. This process applies to all Cohort 1-3 participants and any Cohort 4-9 participants who continue treatment in the extension period.
- Vital signs: blood pressure, pulse rate, body temperature, respiration rate, and weight
- Physical exam (abbreviated/directed)
- Suicidality Questionnaire- C-SSRS since last visit (participants aged ≥ 6 years only)
- Depression and Anxiety Questionnaires (PROMIS or SWYC depending on age of participant)
- Study drug accountability
- Assess for AEs

- Weight-based tildacerfont dose adjustment, if indicated
- For Cohort 4-9 participants, offer continued treatment in extension at Investigator's discretion, re-consent if applicable.

3.1.2.5. Visit 5 (Week 8 ±3 days) (Cohorts 1-3 only)

Visit 5 will be conducted as an outpatient visit. The following activities will be performed:

- Review concomitant medications for any changes
- Pregnancy test for FOCP (urine)
- Safety labs (see [Appendix 1](#))
- Pharmacodynamics (ACTH, 17-OHP, A4, testosterone, and 11KT) drawn prior to GC dosing at approximately 8 AM (±1 hour). Fasting is not required.
- Cortisol
- Tildacerfont concentration (single sample) drawn prior to GC dosing at approximately 8 AM (±1 hour). Fasting is not required.
- GC dosing adjustments to be determined after A4 value is resulted
- Vital Signs: blood pressure, pulse rate, body temperature, respiration rate, and weight
- Physical exam (abbreviated/directed)
- Suicidality Questionnaire- C-SSRS since last visit (participants aged 6- to 17-years only)
- Depression and Anxiety Questionnaires (PROMIS or SWYC depending on age of participant)
- Study drug accountability
- Assess for AEs

3.1.2.6. Visit 6 (EOT for Cohorts 1-3) (Week 12 ±3 days)

Visit 6 will be conducted as an outpatient visit. The following activities will be performed:

- Review concomitant medications for any changes
- Pregnancy test for FOCP (urine)
- Safety labs (see [Appendix 1](#))
- Pharmacodynamics (ACTH, 17-OHP, A4, testosterone, and 11KT) drawn prior to GC dosing at approximately 8 AM (±1 hour). Fasting is not required.
- Cortisol
- Tildacerfont concentration (single sample) drawn prior to GC dosing at approximately 8 AM (±1 hour). Fasting is not required.
- GC dosing adjustments (for Cohort 1-3 patients who are continuing in the EP) to be determined after A4 value is resulted
- Urinalysis
- Vital signs: blood pressure, pulse rate, body temperature, respiration rate, and weight
- Physical exam (full)

- 12-lead ECG
- Suicidality Questionnaire- C-SSRS since last visit (participants aged 6- to 17-years only)
- Depression and Anxiety Questionnaires (PROMIS or SWYC depending on age of participant)
- Study drug accountability
- Assess for AEs

3.1.2.7. Safety Follow-up Visit Telephone Call (30 days after last dose \pm 7 days)

Approximately 30 days after the last dose of study drug (post the 12- or 4-week treatment period, depending on cohort, or post the extension), participants will have a final follow-up visit conducted by telephone. Concomitant medications and AEs will be reviewed. If any ongoing safety issues are identified, the participant may be asked to visit the clinic for additional tests, labs, or assessments.

3.1.2.8. Early Termination Visit

Some study participants may need to end their study participation before completing all of the visits. Participants who end their participation before completing the study will be scheduled for an Early Termination Visit. The following activities will be performed at the clinic:

- Review concomitant medications for any changes
- Pregnancy test for FOCP (urine)
- Safety labs (see [Appendix 1](#) and [Appendix 3](#))
- Pharmacodynamics (ACTH, 17-OHP, A4, testosterone, and 11KT) drawn prior to GC dosing at approximately 8 AM (\pm 1 hour). Fasting is not required.
- Tildacerfont concentration (single sample) drawn prior to GC dosing at approximately 8 AM (\pm 1 hour). Fasting is not required.
- Urinalysis
- Vital signs: blood pressure, pulse rate, body temperature, respiration rate, and weight
- Physical exam (full)
- 12-lead ECG
- Suicidality Questionnaire- C-SSRS since last visit (participants aged \geq 6 years only)
- Depression and Anxiety Questionnaires (PROMIS or SWYC depending on age of participant)
- Study drug accountability
- Assess for AEs

3.1.2.9. End of Study

A participant is considered to have completed the main study treatment period if they completed Visit 6 (Week 12) or Visit 4 (Week 4), depending on cohort. A participant is considered to have completed the study if the participant has completed the Follow-up Visit. The end of the study is defined as the date of the last Follow-up Visit of the last participant in the study.

3.1.3. Extension Period

Participants who complete the 12- or 4-week treatment period, depending on cohort, may be eligible to continue dosing to complete 2 years on treatment in an extension study. Participants will sign a separate informed consent form at Week 12 or Week 4. Pending DMC review, participants in Cohorts 1 and 1a (if indicated) will receive the adult equivalent dose of 200 mg QD during the extension (i.e., Cohort 1 participants will immediately switch to 200 mg equivalent if the DMC has already recommended this dose for Cohort 2, or participants may enter the extension period on 50 mg equivalent and increase to 200 mg equivalent after such a recommendation is made). If a Cohort 1-3 participant is to dose escalate to the 200 mg equivalent, they may do so at the next scheduled visit or come to the clinic for an unscheduled visit and pick up their new supply of study drug. Participants will receive a follow-up phone call 2 weeks after dose escalation to check for AEs.

Further tildacerfont dose adjustments may occur during the extension on a case-by-case basis at the discretion of the Investigator with Sponsor approval. Any extension participant may receive the highest dose recommended by the DMC for their age group. Dose changes (increase or decrease) may occur at a scheduled visit, an unscheduled visit, or via a phone visit, but any dose escalation > 200mg QD will be followed by safety labs (link to list) within 2-4 weeks of the change. Once all participants are in the extension period, safety- data will be reviewed every 6 months by the DMC. Weight-based dose adjustments may be made at any extension visit, with no follow-up labs required.

For Cohorts 1-3, the first visit of the extension will be Week 12. For Cohorts 4-9, Week 4 will be the first extension visit, followed by extension clinic visits at Weeks 8 and 12 (\pm 2 weeks). Starting at Week 12, all participants will attend clinic visits every 12 weeks (\pm 2 weeks).

Approximately a 12-week supply of study drug, as appropriate, will be dispensed at each visit. Approximately 30 days after the last dose of study drug, participants will have a final follow-up visit conducted by telephone. Concomitant medications and AEs will be reviewed. If any ongoing safety issues are identified, the participant may be asked to visit the clinic for additional tests, labs, or assessments.

The extension study visits will include the following:

- Review concomitant medications for any changes
- Physical exam (abbreviated/directed)
- Vital signs: blood pressure, pulse rate, body temperature, respiration rate, and weight
- Safety labs (see [Appendix 2](#) and [Appendix 4](#))
- Pregnancy test for FOCP (urine)
- Urinalysis (Weeks 48 and 96 only)
- Pharmacodynamics (ACTH, 17-OHP, A4, testosterone, and 11KT) drawn prior to GC dosing at approximately 8 AM (\pm 1 hour). Fasting is not required.
- Tildacerfont concentration (single sample)

SPR001-205
Spruce Biosciences, Inc.

CLINICAL STUDY PROTOCOL
Version 5.0

- Study drug accountability
- Suicidality Questionnaire- C-SSRS since last visit (participants aged ≥ 6 years only)
- Depression and Anxiety Questionnaires (PROMIS or SWYC depending on age of participant)
- GC dosing adjustments
- Assess for AEs
- Bone age and predicted adult height calculated from X-ray image of left hand and wrist (every 6 months if deemed appropriate by Investigator, see [Appendix 2](#) and [Appendix 4](#)).
- Tildacerfont dose adjustment as needed (based on recommendation of investigator or due to weight-based dosing changes)

4. STUDY POPULATION**4.1. Eligibility Criteria****4.1.1. Inclusion Criteria**

A participant must meet all of the following criteria to be eligible for this study:

1. Male and female participants aged 2- to 10-years (Cohorts 3, 7, and 9), 11- to -17 years (Cohorts 1, 1a, 2, 6, and 8), and ≥ 18 years (Cohorts 4 and 5) at Screening.
2. For participants aged 2 to 5 years, a minimum weight at Screening of 11 kg.
3. Has a known childhood diagnosis of classic CAH due to 21-hydroxylase deficiency (21-OHD) based on genetic mutation in CYP21A2 and/or documented (at any time) elevated 17-OHP and currently treated with hydrocortisone (HC), HC acetate, prednisone, prednisolone, methylprednisolone (or a combination of these). Other types of CAH may be allowed with Sponsor approval.
4. For participants in Cohorts 4-9, $1.2X \text{ ULN} < A4 < 4X \text{ ULN}$. A4 values outside of this range may be allowed with Medical Monitor (MM) approval.
5. A stable dose of GC replacement for ≥ 1 month before Screening without evidence of non-adherence (as assessed by Investigator). Weight-based dose adjustments or stress dosing in the month prior to Screening are not exclusionary but should be discussed with the MM.
6. For participants on mineralocorticoid replacement, a stable dose for ≥ 1 month prior to Screening.
7. For participants on gonadotropin hormone-releasing hormone (GnRH) analogues, a stable dose initiated ≥ 3 months prior to screening.
8. For participants on aromatase inhibitors, a stable dose for ≥ 3 months prior to screening.
9. If sexually active and capable of reproduction, agrees to follow contraception guidelines (Section 4.2.3).
10. Have provided written informed consent or assent, and/or parent/legal guardian permission, as applicable, prior to undergoing any study procedure, including Screening procedures. The participant and/or parent/legal guardian must be able to read and understand all the study procedures.

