Duration of Participant Participation: Approximately 18 weeks inclusive of Screening, Treatment, and Follow-up for Cohorts 1 to 3; and 10 weeks for Cohorts 4 to 9. The extension period allows for treatment up to 2 years. Please see [Section 3.1.2](#) and [Section 3.1.3](#) for Details on Duration.

Planned Sample Size and Number of Sites: The study is expected to enroll approximately 20 children across the first 3 cohorts (i.e., Cohorts 1, 2, and 3), 10 in the 11-to 17- year age group and 10 in the 2-to 10- year age group. If the optional Cohort 1a is initiated (up to 5 participants), however, Cohorts 1 to 3 may enroll up to 25 children total, 15 in the 11-to 17-year-old age group and 10 in the 2-to 10-year-old age group.

Up to an additional six cohorts (Cohorts 4-9) are planned to investigate BID dosing over 4 weeks of treatment. The study will also enroll up to approximately 15 adults aged ≥ 18 years across Cohorts 4 and 5; and up to approximately 30 children across 4 additional cohorts [up to 15 in the 11- to 17-year age group (Cohorts 6 and 8) and up to 15 in the 2- to 10-year age group (Cohorts 7 and 9)].

If all possible doses are studied, total sample size of this study may be up to approximately 55 children and 15 adults. Please see Table S-1 for subject numbers by dosing cohort:

Table S-1

Cohorts:	Ages (years):	Corresponding Adult Dose	Subject Numbers:
1	11-17	50 mg QD	5
1a	11-17	To be determined based on DMC recommendation (50 or 100 mg QD)	5
2	11-17	200 mg QD	5
3	2-10	50 mg QD, 100 mg QD, OR 200 mg QD	10
4	≥ 18	200 mg BID	5
5	≥ 18	300 mg BID and/or 400 mg BID	5+5 ¹
6	11-17	200 mg BID	5
7	2-10	200 mg BID	5
8	11-17	300 mg BID and/or 400 mg BID	5+5 ¹
9	2-10	300 mg BID and/or 400 mg BID	5+5 ¹
			Up to 70 subjects total

¹+5 allows for the option of dosing 300mg before or after 400 mg Cohort is initiated if indicated by the DMC

The study will be conducted at approximately 15 investigative sites within North America. Please see [Section 8.1](#) for details on Planned Sample size.

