Starting on Day 15, Cohorts 1 and 2 will switch to taking the study drug with their evening meal for the duration of the study.

Cohort 3 dosing:

Cohort 3 will dose with a morning meal at the study clinic on Day 1 (Visit 2) to allow for a 1-hour observational period. All subsequent doses for Cohort 3 will occur with evening meals.

APPENDIX 2. SCHEDULE OF ACTIVITIES FOR OPEN-LABEL EXTENSION FOR COHORTS 1, 1A, 2, AND 3

	Week 12	Week 24	Week 36	Week 48	Week 60	Week 72	Week 84	Week 96 (EOT)	Early Termination	Safety Follow-up (Phone call)
VISIT NUMBER	6	7	8	9	10	11	12	13		
Visit windows	±2 weeks		Last dose +30 days							
Informed consent/assent	X									
Concomitant medications	X	X	X	X	X	X	X	X	X	X
Pregnancy test for FOCP ¹	X	X	X	X	X	X	X	X	X	
Laboratory assessments ^{2,3}	X	X	X	X	X	X	X	X	X	X ⁴
PD and tildacerfont samples ⁵	X	X	X	X	X	X	X	X	X	X ⁴
A4-based GC dose adjustment ⁶	X	X	X	X	X	X	X	X		
Weight-based tildacerfont dose adjustment	X	X	X	X	X	X	X	X		
Urinalysis ⁷				X		X		X	X	X ⁴
Vital signs ⁸ , body weight	X	X	X	X	X	X	X	X	X	X ⁴
Abbreviated/directed physical exam	X	X	X	X	X	X	X	X	X	X ⁴
C-SSRS ⁹	X	X	X	X	X	X	X	X	X	X ⁴
PROMIS ¹⁰	X	X	X	X	X	X	X	X	X	X ⁴
SWYC ¹¹	X	X	X	X	X	X	X	X	X	

SPR001-205

Spruce Biosciences, Inc.

CLINICAL STUDY PROTOCOL

Version 5.0

	Week 12	Week 24	Week 36	Week 48	Week 60	Week 72	Week 84	Week 96 (EOT)	Early Termination	Safety Follow- up (Phone call)
VISIT NUMBER	6	7	8	9	10	11	12	13		
Visit windows	±2 weeks		Last dose +30 days							
Bone age and predicted adult height ¹²		X		X		X		X		
Dispense study drug	X	X	X	X	X	X	X	X		
Review any AEs	X	X	X	X	X	X	X	X	X	X
Study drug accountability	X	X	X	X	X	X	X	X	X	

Abbreviations: 11KT=11-ketotestosterone; A4=androstenedione; ACTH=adrenocorticotropin hormone; AEs=adverse events; ALT=alanine aminotransferase; ALP=alkaline phosphatase; AST=aspartate aminotransferase; C-SSRS=Columbia–Suicide Severity Rating Scale; ECG=electrocardiogram; EOT= end of treatment; ET=early termination; FOCP=female of childbearing potential; GC=glucocorticoid; GGT=gamma-glutamyl transferase; PD=pharmacodynamics; PROMIS= Patient Reported Outcomes Measurement Information System; 17-OHP=17-hydroxyprogesterone; SWYC=Survey of Well-being of Young Children; T=testosterone.

¹ A serum pregnancy test will be performed at Screening for FOCP only. All subsequent tests will be urine pregnancy tests

² Labs will be drawn at 8 AM (±1 h) before any morning dose of GC medication.

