Weight/Efficacy Tildacerfont Dose Adjustment	X		X	X	X	X	X	X	X			
Dispense study drug	X	X	X	X	X	X	X	X	X			
Review any AEs	X	X	X	X	X	X	X	X	X	X	X	X
Study drug accountability	X	X	X	X	X	X	X	X	X	X	X	

Abbreviations: 11KT=11-ketotestosterone; A4=androstenedione; ACTH=adrenocorticotropin hormone; AEs=adverse events; ALT=alanine aminotransferase; ALP=alkaline phosphatase; AST=aspartate aminotransferase; C-SSRS=Columbia–Suicide Severity Rating Scale; ECG=electrocardiogram; EOT= end of treatment; ET=early termination; FOCP=female of childbearing potential; GC=glucocorticoid; GGT=gamma-glutamyl transferase; PD=pharmacodynamics; PROMIS= Patient Reported Outcomes Measurement Information System; 17-OHP=17-hydroxyprogesterone; SWYC=Survey of Well-being of Young Children; T=testosterone.

¹ A serum pregnancy test will be performed at Screening for FOCP only. All subsequent tests will be urine pregnancy tests

² Labs will be drawn at 8 AM (±1 h) before any morning dose of GC medication.

³ Laboratory assessments include: hematology, chemistry (including liver function tests AST, ALT, ALP, GGT, total and direct bilirubin, and total bile acids), thyroid panel. Fasting is not required.

⁴ As needed based upon any safety concerns, per Investigator discretion.

⁵ PD Samples (ACTH, 17-OHP, A4, testosterone, and 11KT). They must be drawn prior to GC dosing. Fasting is not required. Single samples for plasma concentration of tildacerfont will be drawn at all visits.

⁶ GC dose (frequency or total daily dose) may be adjusted based on A4 levels collected at each visit. If a change in GC is warranted by the A4 algorithm, sites will contact participants by telephone after receipt of results (within approximately 2 weeks) after each applicable study visit.

⁷ Urinalysis should include the following: specific gravity, pH, glucose, protein, blood, ketones, bilirubin, urobilinogen, nitrite, by dipstick. Microscopic examination should be obtained if blood or protein is abnormal.

⁸ Systolic and diastolic blood pressure, pulse rate, body temperature, and respiration rate.

⁹ The C-SSRS, to assess suicidality, is only conducted for participants aged ≥6 years.

¹⁰ PROMIS, to assess anxiety and depression, is conducted for participants aged ≥5 years.

¹¹ The SWYC to assess anxiety and depression is only conducted in Cohort 7 (and 9 if indicated) for participants ≤5 years of age.

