**Table 9 Schedule of Activities for Open-label Extension for Cohorts 1, 1a, 2, and 3**

	Week 12	Week 24	Week 36	Week 48	Week 60	Week 72	Week 84	Week 96 (EOT)	Early Termination	Safety Follow-up (Phone call)
VISIT NUMBER	6	7	8	9	10	11	12	13		
Visit windows	±2 weeks		Last dose +30 days							
Informed consent/assent	X									
Concomitant medications	X	X	X	X	X	X	X	X	X	X
Pregnancy test for FOCP 	X	X	X	X	X	X	X	X	X	
Laboratory assessments 	X	X	X	X	X	X	X	X	X	X 
PD and tildacerfont samples 	X	X	X	X	X	X	X	X	X	X 
A4-based GC dose adjustment 	X	X	X	X	X	X	X			
Weight-based tildacerfont dose adjustment	X	X	X	X	X	X	X			
Urinalysis 				X		X		X	X	X 
Vital signs  , body weight	X	X	X	X	X	X	X	X	X	X 
Abbreviated/directed physical exam	X	X	X	X	X	X	X	X	X	X 
C-SSRS 	X	X	X	X	X	X	X	X	X	X 
PROMIS 	X	X	X	X	X	X	X	X	X	X 
SWYC 	X	X	X	X	X	X	X	X	X	
Bone age and predicted adult height 		X		X		X		X		
Dispense study drug	X	X	X	X	X	X	X			
Review any AEs	X	X	X	X	X	X	X	X	X	X
Study drug accountability	X	X	X	X	X	X	X	X	X	

Abbreviations: 11KT=11-ketotestosterone; A4=androstenedione; ACTH=adrenocorticotropin hormone; AEs=adverse events; ALT=alanine aminotransferase; ALP=alkaline phosphatase; AST=aspartate aminotransferase; C-SSRS=Columbia–Suicide Severity Rating Scale; ECG=electrocardiogram; EOT=end of treatment; ET=early termination; FOCP=female of childbearing potential; GC=glucocorticoid; GGT=gamma-glutamyl transferase; PD=pharmacodynamics; PROMIS= Patient Reported Outcomes Measurement Information System; 17-OHP=17-hydroxyprogesterone; SWYC=Survey of Well-being of Young Children; T=testosterone.

 A serum pregnancy test will be performed at Screening for FOCP only. All subsequent tests will be urine pregnancy tests

 Labs will be drawn at 8 AM (±1 h) before any morning dose of GC medication.

 Laboratory assessments include: hematology, chemistry (including liver function tests AST, ALT, ALP, GGT, total and direct bilirubin, and total bile acids), thyroid panel. Fasting is not required.

 As needed based upon any safety concerns, per Investigator discretion.

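### The documents disagree on whether study drug is dispensed at Week 96, the extension's end-of-treatment visit, and so on when extension treatment and its clinic monitoring end

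*Protocol*

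**What the plan says.** Protocol Section 3.1.3 covers the extension for all cohorts. It says of supply: "Approximately a 12-week supply of study drug, as appropriate, will be dispensed at each visit". It sets clinic visits at 12-week intervals from Week 12 ("all participants will attend clinic visits every 12 weeks"), with a window of 2 weeks either side. It says that participants "may be eligible to continue dosing to complete 2 years on treatment in an extension study", and the synopsis adds: "The extension period allows for treatment up to 2 years".

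Four schedules then show the visits:

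- Protocol Appendix 2 (Cohorts 1-3) runs from Week 12 to Week 96, and Week 96 is labelled EOT. Its supply row reads "Dispense study drug X X X X X X X X", so the eighth mark falls at Week 96. The weight-based tildacerfont adjustment row is also marked at Week 96.
- SAP Table 9 covers the same cohorts and visits. Its row reads "Dispense study drug X X X X X X X", so the last mark is at Week 84. Its tildacerfont adjustment row also ends at Week 84.
- Protocol Appendix 4 (Cohorts 4-9) starts at Week 4. Its row reads "Dispense study drug X X X X X X X X X", nine marks ending at Week 84, and tildacerfont adjustment also ends there.
- SAP Table 11 matches Appendix 4.

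After Week 96 the only scheduled contact is a telephone call about 30 days after the last dose. The follow-up column of Appendix 2 allows laboratory tests, PD samples, vital signs, C-SSRS and PROMIS as needed. It has no mark for a pregnancy test or SWYC.

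**The concern.** A visit labelled end of treatment should not also supply drug or adjust its dose unless dosing is meant to continue. Appendix 2 does both, and Section 3.1.3 read literally agrees with it. The other three schedules do not.

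Sites dispense from the protocol. If they follow Appendix 2, children in Cohorts 1-3 who stay in the extension could take drug after their last scheduled clinic assessment. What would then be unscheduled is what the protocol relies on for safety:

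- **Liver:** Section 6.1.2 calls for continued clinical monitoring because of the bile salt export pump findings, and its stopping rules need laboratory results.
- **Psychiatric:** the C-SSRS, PROMIS and SWYC drive or support the rules in Sections 6.1.5 and 6.1.6.
- **Pregnancy:** Section 1.3 names developmental toxicity as a preclinical risk.
- **Accountability:** Section 5.2.4 has leftover drug returned at visits, and none is scheduled after Week 96.

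The last-dose date also closes the period for treatment-emergent adverse events (30 days later), and AEs and SAEs are the extension's primary endpoint.

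**Working it through.** No sample-size or power figure is involved. The check compares the rows and then does calendar arithmetic.

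**Step 1. Rows side by side**

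| Schedule | Cohorts | Dispensing | Tildacerfont adjustment | A4-based GC adjustment |
|---|---|---|---|---|
| Protocol Appendix 2 | 1-3 | 8 marks, Weeks 12 to 96 | 8 marks, Weeks 12 to 96 | 8 marks, Weeks 12 to 96 |
| SAP Table 9 | 1-3 | 7 marks, Weeks 12 to 84 | 7 marks, Weeks 12 to 84 | 7 marks, Weeks 12 to 84 |
| Protocol Appendix 4 | 4-9 | 9 marks, Weeks 4 to 84 | last mark Week 84 | 10 marks, Weeks 4 to 96 |
| SAP Table 11 | 4-9 | 9 marks, Weeks 4 to 84 | last mark Week 84 | 10 marks, Weeks 4 to 96 |

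Appendix 2 and SAP Table 9 differ in exactly these three rows. Their other rows carry the same marks.

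**Step 2. End dates the documents can support**

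Inputs: last clinic visit Week 96 (Appendix 2); supply about 12 weeks and limit 2 years (Section 3.1.3). The 2 years are counted from first dose.

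- No dispensing at Week 96: the Week 84 supply lasts to 84 + 12 = Week 96, which fits the EOT label. 96 × 7 / 365.25 = 1.84 years.
- Dosing to 2 years: 2 × 365.25 / 7 = 104.4 weeks, which is 104.4 − 96 = 8.4 weeks after the last clinic visit. Some supply at Week 96 would be needed.
- A full supply at Week 96, all taken: 96 + 12 = Week 108 (106 to 110 with the visit window). That is 12 weeks after the last clinic visit and 108 − 104.4 = 3.6 weeks past the 2-year mark.

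So the SAP Table 9 marks fit the EOT label, and the Appendix 2 marks fit the 2-year wording. The two sets cannot both stand.

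**Step 3. Effect on the follow-up call**

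30 days = 30 / 7 = 4.3 weeks. The call, and the close of the treatment-emergent period, falls at about Week 100.3, 108.7 or 112.3 for last doses at Weeks 96, 104.4 and 108.

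**The case against.** **The supply sentence is qualified.** It allows for a smaller quantity, or none, at a final visit, and the same section limits treatment to 2 years. This stands. A reader might infer that the protocol permits dosing to Week 108. It does not: Week 108 is only how long a full supply would last, and it would breach the 2-year limit. But the qualifier gives sites no way to choose between no supply, about 8 weeks and about 12 weeks at Week 96, and it does not explain the Appendix 2 marks.

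**Up to 2 years is a ceiling.** A 96-week schedule satisfies the synopsis wording, and Section 3.1.3 speaks only of eligibility. This also stands. The tension lies with the phrase about completing 2 years.

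**Monitoring does not vanish.** A reader might infer that nothing is scheduled after Week 96. The telephone follow-up is scheduled, it can lead to a clinic visit and tests, participants are encouraged to report events between visits (Section 7.2.4), and the DMC reviews extension safety data every 6 months. All of this stands. None of it is a scheduled clinic assessment while on drug.

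**The GC row proves nothing.** Glucocorticoid is background therapy that continues without study drug, and Appendix 4 and SAP Table 11 also mark its adjustment at Week 96. This is accepted. The point rests on dispensing and tildacerfont adjustment alone.

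**The marks may be an artefact of reading the PDF.** Other rows are visibly disturbed. Clinic drug administration in Appendix 1 appears under Weeks 2 and 4, against Day 1 and Week 2 in SAP Table 8. The adverse-event rows also differ in count between copies (6 against 7 marks for Cohorts 1-3). A count difference alone is therefore not proof. An extra mark in exactly the three rows tied to continued treatment, with all other rows agreeing, makes an artefact unlikely but does not exclude it.

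**The SAP settles it.** SAP Section 4 gives the SAP precedence only for planned analyses and leaves the extension analysis to a separate SAP. It does not direct dispensing at sites.

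**Conclusion.** The inconsistency is real. Appendix 2 and a literal reading of Section 3.1.3 supply drug at the visit labelled EOT, while SAP Table 9, Appendix 4 and SAP Table 11 stop at Week 84. Because Section 3.1.3 applies to all cohorts, it conflicts with Appendix 4 as well. The 2-year wording points to about Week 104, while the schedule ends treatment and scheduled clinic monitoring at Week 96.

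If drug is dispensed at Week 96 and used, the time on drug without a scheduled clinic visit, laboratory tests, psychiatric scales or pregnancy test is about 8 weeks to the 2-year limit, or up to 12 weeks if a full supply were used. This assumes that the Week 96 marks are as extracted, that the 2 years run from first dose, and that the visit falls on its target week.

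The number of children affected cannot be given. The extension is optional, and the documents do not say how many will reach Week 96. No analysis in this SAP depends on the point. It concerns participant safety and site conduct, and it is worth correcting because the cost is small.

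**What to change.** First check the Week 96 marks in Appendix 2 against the source PDF. Then reconcile Protocol Section 3.1.3, Appendices 2 and 4, and SAP Tables 9 and 11 so that these all agree:

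- the end of extension treatment;
- the EOT label;
- the dispensing and tildacerfont adjustment marks;
- the 2-year wording in Section 3.1.3 and the synopsis;
- the scheduled safety monitoring up to that end date.

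Which end date is right is for the sponsor to decide; the GC adjustment marks need not follow it. The cost is wording and table corrections in the protocol and SAP. The reconciliation itself adds no data collection; any visit added would follow from the sponsor's choice of end date.
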